3. PARTICIPANT SELECTION

Patients will be identified at the weekly Gynecologic Oncology-Pathology Multidisciplinary Tumor Board that routinely reviews all gynecologic cancer pathology in patients operated at

CONFIDENTIAL

This document is confidential. Do not disclose or use except as authorized.

Massachusetts General Hospital (MGH). Potentially eligible patients operated elsewhere and referred for adjuvant treatment to MGH would be identified based on pathology review of submitted histologic sections from the referring institution.

3.1 Eligibility Criteria

Participants must meet the following criteria on screening examination to be eligible to participate in the study:

3.1.1 Participants must have histologically confirmed primary cancer of the uterus or cervix with histologically confirmed metastasis to one or more parametrial, pelvic, or para-aortic nodes prior to enrollment. Participants diagnosed at other institutions must have pathology reviewed and confirmed at MGH or another DF/HCC institution.

3.1.1.a Uterine cancer participants will be FIGO stage IIIC and may have endometrioid cancer, clear cell cancer, uterine papillary serous cancer, carcinosarcoma, or endometrial stromal sarcoma.

3.1.1.b Cervical cancer participants will be AJCC stages pT_{1,2},N₁,M₀ with squamous carcinoma, adenocarcinoma, adenosquamous carcinoma, or glassy cell carcinoma histology.

3.1.2 Participants must have undergone simple, modified radical, or radical abdominal hysterectomy or vaginal hysterectomy and lymphadenectomy (pelvic nodes, para-aortic nodes, or both nodal basins) by open or laparoscopic assisted technique.

3.1.3 Participants may have undergone prior chemotherapy for their uterine malignancy or may undergo chemotherapy in conjunction with adjuvant proton therapy per discretion of treating physicians. The agents, doses, routes and schedule of administration will be determined by their attending Gynecologic Oncologist or Medical Oncologist. For participants who have undergone prior chemotherapy, protocol radiation may commence no sooner than 21 days after the last chemotherapy treatment.

3.1.4 Participants with cervical cancer may undergo chemotherapy in conjunction with adjuvant proton therapy. The agents, doses, routes and schedule of administration will be determined by their attending Gynecologic Oncologist or Medical Oncologist.

3.1.5 Prior therapeutic radiation exposure to tissues for which protocol irradiation is anticipated is an exclusion criterion.

3.1.6 There will be no upper age limit for eligibility. Elderly patients will be eligible for participation provided they are competent to provide informed consent, or written consent can be provided by their duly appointed healthcare proxy.

CONFIDENTIAL

This document is confidential. Do not disclose or use except as authorized.

3.1.7 Life expectancy of greater than 18 months.

3.1.8 ECOG performance status ≤ 2 (Karnofsky $\geq 60\%$, see Appendix A).

3.1.9 Baseline hematology laboratories will be performed prior to registration, the patient can be enrolled in the trial if laboratory values are deemed clinically acceptable by treating physician.

3.1.10 Participants must have no clinical, radiographic, or laboratory evidence of cancer dissemination to the peritoneal cavity, chest cavity, or spread via hematogenous dissemination. CT or PET/CT of the chest, abdomen and pelvis must have been obtained within 10 weeks of study entry. There must be no measurable (macroscopic) disease within the radiation target volume following hysterectomy and lymphadenectomy.

3.1.11 Participants must have the ability to understand and the willingness to sign a written informed consent document.

CONFIDENTIAL

This document is confidential. Do not disclose or use except as authorized.

3.2 Exclusion Criteria

- 3.2.1 Inability to sign informed consent document.
- 3.2.2 Evidence of extra-abdominal cancer dissemination or hematogenous cancer dissemination.
- 3.2.3 Evidence of measurable (macroscopic) residual disease following hysterectomy and lymphadenectomy.
- 3.2.4 Prior therapeutic radiation to target tissues for protocol radiation.
- 3.2.5 Individuals with a history of a different malignancy are ineligible except for the following circumstances. Individuals with a history of other malignancies are eligible if they have been disease-free for at least 5 years or are deemed by the investigator to be at low risk for recurrence of that malignancy. Individuals with the following cancers are eligible if diagnosed and treated within the past 5 years: cervical cancer *in situ*, and basal cell or squamous cell carcinoma of the skin.
- 3.2.6 Age less than 18.

3.3 Inclusion of Women, Minorities and Other Underrepresented Populations

All participants are women. Eligibility criteria otherwise do not limit or impede participation or retention of minorities or underrepresented populations.

4. REGISTRATION PROCEDURES

4.1 General Guidelines for DF/HCC and DF/PCC Institutions

Institutions will register eligible participants with the ODQ in the Clinical Trials Management System (CTMS) OnCore. Registration must occur prior to the initiation of therapy. Any participant not registered to the protocol before treatment begins will be considered ineligible and registration will be denied.

A member of the study team will confirm eligibility criteria and complete the protocol-specific eligibility checklist.

CONFIDENTIAL

This document is confidential. Do not disclose or use except as authorized.

Following registration, participants may begin protocol treatment. Issues that would cause treatment delays should be discussed with the Principal Investigator. If a participant does not receive protocol therapy following registration, the participant's protocol status must be changed. Registration cancellations must be made in OnCore as soon as possible.

4.2 Registration Process for DF/HCC and DF/PCC Institutions

DF/HCC Standard Operating Procedure for Human Subject Research titled *Subject Protocol Registration* (SOP #: REGIST-101) must be followed.

5. TREATMENT PLAN

Treatment will be administered on an outpatient basis. Expected toxicities and potential risks as well as dose modifications for proton beam teletherapy are described in Section 6 (Expected Toxicities and Dosing Delays/Dose Modifications). No investigational agents or therapies other than those described below may be administered with the intent to treat the participant's malignancy.

5.1 Pre-treatment Criteria

5.1.1 Day 1 proton beam teletherapy: Provided all laboratory determinations and imaging findings specified in section 3.1 are within the protocol eligibility requirements, no further pre-treatment criteria are established.

5.1.2 Subsequent proton beam teletherapy treatments 2-30: Maintenance of platelet count \geq 35,000/mcL and absolute neutrophil count \geq 800/mcL.

5.1.3 Uterine cancer patients who have received chemotherapy prior to proton therapy may have twice-weekly complete circulating blood counts commencing on or before treatment fraction 8. These labs will be ordered and monitored at the discretion of the treating physician.

5.1.4 Cervix cancer patients may have weekly complete blood counts commencing on or before treatment fraction 8. Cervix patients receiving concurrent chemotherapy will have weekly determination of serum electrolytes, renal function, Ca++, and Mg++. These labs will be ordered and monitored at the discretion of the treating physician.

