7. DRUG FORMULATION AND ADMINISTRATION: N/A

8. CORRELATIVE/SPECIAL STUDIES: N/A

9. STUDY CALENDAR

9.1 Baseline hematologic evaluations are to be conducted within 2-weeks prior to study entry. Scans must be done \leq 10 weeks prior to study entry.

9.2 Patients will be interviewed and examined weekly during treatment.

9.3 Routine surveillance follow-up will be: 3, 6, 9, 12, 15, 18, 21, 24, 28, 32, 36, 42, 48, 54 and 60 months (+/- 4 weeks) following adjuvant radiation treatment.

CONFIDENTIAL

This document is confidential. Do not disclose or use except as authorized.

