9.4 Study Calendar/Required Data

Tests and Observations	At Study Entry	During Treatment	At Follow Up (1)
Informed Consent	x		
History	x		x
Concurrent Meds	x	x	x
Physical Exam (2)	x	x	x
Pelvic Exam (3)	x	x	x
CBC with diff, PLT (4)	x	x	
Serum Chemistries (5)	x	x	
Toxicity and AE evaluation	x	x	x
Radiological imaging (6)	x		x
Quality of Life (7)	x		x

Notes:

- (1) Follow up schedule (+/- 4 weeks for each time point): every 3 months for 2 years; every 4 months to year 3; every 6 months until year 5.
- (2) Physical includes, weight, vitals, performance status required at baseline. For weekly on-treatment and follow up visits, physical exam will be performed as pertinent at the discretion of the treating physician, and includes weight. .
- (3) Pelvic Exam pre-study, during vaginal brachytherapy (typically week 6 of treatment) and at each follow up visit
- (4) Study entry labs for pre-treatment must be done within 14 days of study entry. Labs may be repeated twice weekly for uterine cancer patients, once weekly for cervix cancer patients during treatment to ensure maintenance of platelets >35,000mcL and ANC >800mcL. These labs are ordered and monitored at the discretion of the treating physician.
- (5) Required chemistries are: Albumin, Alk Phos, T bili, BUN, bicarbonate, chloride, creatinine, glucose, LDH, phosphorus, potassium, total protein, SGOT, SGPT, sodium, calcium, magnesium. These will be ordered and monitored at the discretion of the treating physician.
- (6) Contrast enhanced CT scan of the chest, abdomen and pelvis pre-study (\leq 10 weeks of study entry) and in post treatment, twice per year to year 3.
- (7) Quality of Life will be assessed using the FACT-En Version 4 (Appendix 2) instrument for uterine patients and the FACT-Cx Version 4 (Appendix 3) instrument for cervix patients. QOL will be assessed at study entry, and at 6, 12, 24, 36, 48, and 60 months (+/- 4 weeks) after protocol therapy.

10. MEASUREMENT OF EFFECT: Participants are excluded if they have measurable disease following hysterectomy. (3.2.2, 3.2.3)

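### Fraction 1 has no numeric blood-count limit and no count is required between the entry sample and fraction 1, so a patient can start protons after chemotherapy without a count that shows recovery

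*Combined protocol and SAP*

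**What the plan says.** - **Fraction 1.** Section 5.1.1 relies on the section 3.1 requirements; once these are met, "are within the protocol eligibility requirements, no further pre-treatment criteria are established". The haematology item there, 3.1.9, requires baseline tests before registration and states that "the patient can be enrolled in the trial if laboratory values are deemed clinically acceptable by treating physician". It sets no platelet or neutrophil value.
- **Later fractions.** Section 5.1.2 begins "Subsequent proton beam teletherapy treatments 2-30: Maintenance of platelet count" and sets platelets at 35,000/mcL or more and ANC at 800/mcL or more.
- **Date of the required count.** Section 9.1: "Baseline hematologic evaluations are to be conducted within 2-weeks prior to study entry". Calendar note 4 in section 9.4 agrees: "Study entry labs for pre-treatment must be done within 14 days of study entry". Both are tied to entry, not to fraction 1.
- **Entry to fraction 1.** Section 4.1 requires registration before therapy and adds "Issues that would cause treatment delays should be discussed with the Principal Investigator". It gives no maximum interval.
- **After chemotherapy.** Section 3.1.3: "protocol radiation may commence no sooner than 21 days after the last chemotherapy treatment". No recovery of counts is required.
- **On treatment.** Under 5.1.3, uterine patients who had chemotherapy "may have twice-weekly complete circulating blood counts commencing on or before treatment fraction 8", at the treating physician's discretion. Section 6.2.2 suspends treatment for uterine patients at the same two limits, without naming a fraction.

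**The concern.** Section 2.2.1 describes uterine patients as commonly reaching radiation after 4-6 cycles of carboplatin and taxol. The protocol has decided at what platelet and neutrophil values a fraction should not be given, but 5.1.2 applies those values from fraction 2. The only required count is dated to a different event, study entry, and may be too close to the last chemotherapy dose, or even before it, to show recovery. At stake is the safety of a few patients: one could start pelvic or extended-field radiation below the protocol's own limits, with every dated rule followed and nobody aware of it.

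**Working it through.** The plan states no figure to reproduce here. The check reads the rules together and then does calendar arithmetic.

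**Step 1: the rules side by side**

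| Rule | Fractions covered | Numeric limit | Count required, and when |
|---|---|---|---|
| 5.1.1 with 3.1.9, 9.1, note 4 | 1 | None; physician judgement | Yes, within 14 days before entry |
| 5.1.2 | 2-30 | Platelets 35,000; ANC 800 | None stated |
| 6.2.2 (uterine) | Not stated | The same | None stated |
| 5.1.3, 5.1.4, 6.2.3, note 4 | On treatment | None of their own, except that note 4 repeats the two values | Discretionary, from fraction 8 or before |

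The Lab Form (12.1.2) is due with the baseline form and weekly during treatment. That schedule ties no sample to fraction 1, and the clinical text leaves on-treatment counts to the physician. So on any reading, no row requires a count between the entry sample and fraction 1.

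**Step 2: how old the required count can be**

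Inputs:
- 14 days: oldest permitted count before entry (9.1, note 4).
- W: days from last chemotherapy to fraction 1; minimum 21 (3.1.3). A 28-day value is added for comparison.
- g: days from entry to fraction 1. The documents do not give it, so 0, 7 and 14 are assumed.

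Formulas:
- Age of the count at fraction 1 = 14 + g.
- Day of the count relative to the last dose = W - g - 14 (negative means before the last dose).

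| W | g | Entry, days after last dose (W - g) | Age of count at fraction 1 | Day of count relative to last dose |
|---|---|---|---|---|
| 21 | 0 | 21 | 14 | +7 |
| 21 | 7 | 14 | 21 | 0 |
| 21 | 14 | 7 | 28 | -7 |
| 28 | 0 | 28 | 14 | +14 |
| 28 | 7 | 21 | 21 | +7 |
| 28 | 14 | 14 | 28 | 0 |

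These are bounds. Each row takes the oldest count the rules allow.

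**Step 3: effect of a 7-day window before fraction 1**

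The earliest qualifying count falls on day W - 7 after the last dose: 21 - 7 = 14, or 28 - 7 = 21.

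**Step 4: patients reached (section 14.2, position at October 2016)**

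- Still to enroll: 22 - (9 + 5) = 8.
- Uterine: about 14 - 9 = 5.
- Cervical: about 8 - 5 = 3.

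Pre-radiation chemotherapy is described for uterine patients (5.2.20a), and it is optional. The new count therefore concerns about 5 patients.

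**The case against.** The strongest reply is that fraction 1 is already gated. A baseline count is mandatory, the physician must find it acceptable, and 5.1.1 carries that requirement to Day 1. This stands: what is missing is a number and a date, not a check of any kind.

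Second, 6.2.2 names no fraction and can be read to hold fraction 1 in a uterine patient known to be below the limits. This also stands, although 6.2.2 speaks of suspending treatment and 5.1.1 denies further criteria. It does not close the gap, because a limit cannot act on a count that nobody has taken.

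Third, the contrast between fractions 1 and 2 is weaker than it looks. With on-treatment counts discretionary, fractions 2-7 can also be given unmeasured. Leaving the timing of counts to the physician is consistent across the protocol, so a fixed window is partly a matter of preference. This is fair and keeps the point minor.

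A reader might go further and infer that carry-over from chemotherapy will be counted as proton toxicity and distort the results. The documents do not support that. No haematologic rate is an endpoint, and section 14.1 puts the emphasis on GI toxicity. Under 11.2.1 an abnormal laboratory value is an adverse event only if it causes symptoms or signs or calls for treatment or further tests, and 11.2.4 allows an event to be graded as unlikely or unrelated.

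**Conclusion.** The concern holds as a minor patient-safety point. Read together, the rules let a patient start fraction 1 after chemotherapy without a count that shows recovery from the last cycle. With the 21-day minimum and same-day entry, the required count may be 14 days old and date from day 7 after the last dose. The earlier dates in the table depend on an entry-to-fraction-1 gap that is assumed, and they are worst cases, not a description of expected practice. The documents give no basis for estimating how often a count would in fact be below the limits at fraction 1.

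The table might suggest that patients are regularly started below the limits. It shows only what the rules permit, and treating physicians may well check counts anyway. Nothing here calls for a new haematologic baseline in the toxicity analysis of 14.5.1.

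**What to change.** 1. In 5.1.2, change the range to treatments 1-30.
2. In 5.1.1, 9.1 and calendar note 4, require for patients who had pre-radiation chemotherapy a CBC with differential after the last cycle and within about 7 days before fraction 1. The entry CBC serves if it meets both conditions.
3. If either limit is not met, defer fraction 1 and repeat the count until both are.

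The 7 days are a judgement; combined with the 21-day minimum they place the count at least 14 days after the last dose. On-treatment counts can stay discretionary.

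The cost is a wording amendment, one routine CBC in the few patients whose entry count does not qualify (about 5 at most), repeat counts if a value is low, and an occasional short deferral. Section 5.5 already accepts a break of any length for counts to recover. It is written for breaks once treatment has begun, so the amendment should state that a deferred start is allowed too.

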5.2 Agent Administration

CONFIDENTIAL

This document is confidential. Do not disclose or use except as authorized.

5.2.1 Proton beam therapy will be planned based on patient supine CT simulation with custom immobilization per standard practice in the Department of Radiation Oncology, Massachusetts General Hospital.

5.2.2 Full contours will be obtained for all abdominal organs at risk including: stomach, duodenum, bowel (small bowel will be contoured separately if patient requires boost with teletherapy), rectum, liver, kidneys, spinal cord, thoraco-lumbar spine T12-L5, pelvic bone girdle, and proximal femurs from the femoral heads to below the lesser trochanters.

5.2.3 Comparative treatments plans for IMRT and 3DCRT will be generated for each participant from the same CT-simulation data set for comparison purposes and for actual treatment of participants in the event of the proton beam being unavailable for any reason longer than 2 working days.

5.2.4 Standard immobilization-stabilization procedures and treatment verification procedures will be employed as customarily performed for patients at the FHBPTC.

5.2.5 For participants undergoing proton beam therapy to the pelvis, the superior extent of the target volume will be at the interspace of the fifth lumbar vertebra and the first sacral segment (L5-S1).

5.2.6 For participants undergoing proton beam therapy to an extended volume (pelvic and para-aortic nodal basins) the superior border will be at the interspace of the twelfth thoracic and the first lumbar vertebrae (T12-L1).

5.2.7 For participants treated for cervical cancer the inferior extent of the target volume will encompass the proximal 2 cm of the vagina.

5.2.8 For participants treated for uterine cancer, the inferior extent of the target volume will encompass the full extent of the vagina from the apex to the introitus defined as the external urethral meatus.

5.2.9 All proton beam teletherapy treatments will be administered at a daily dose of 1.8 Gy (RBE). The RBE for proton radiation is set at 1.1. The dose unit Gy (RBE) is defined as the proton dose in Gy x RBE 1.1.

5.2.10 All proton beam teletherapy treatments will be administered no more than 5 treatment days per week.

5.2.11 Total absorbed teletherapy dose will be 45 Gy (RBE) in 25 daily fractions of 1.8 Gy (RBE) over 6 weeks for all participants except as noted in 5.2.12.

5.2.12 For patients with extra-nodal extension and cancer extension to adjacent structures (bone, artery, vein, muscle, nerve, bladder serosa, rectal serosa) reduced volume(s) may be treated with proton beam to 54 Gy (RBE) in 30 fractions of 1.8 Gy (RBE) over 7 weeks.

5.2.13 Participants with cervical cancer who have more than two positive pelvic lymph nodes or

CONFIDENTIAL

This document is confidential. Do not disclose or use except as authorized.

extranodal involvement may be treated with a pelvic and para-aortic radiation field.

5.2.14 Target coverage requirements

- $V_{90} \geq 90\% \text{ (40.5 Gy (RBE))}$
- $D_{97}(43.65 \text{ Gy (RBE)}) \geq 97\%$
- $D_{99}(44.55 \text{ Gy (RBE)}) \geq 90\%$
- $D_{110}(49.5 \text{ Gy (RBE)}) \leq 10\%$
- $D_{115}(51.75 \text{ Gy (RBE)}) \leq 1\%$
- Dose maximum should occur within the PTV

For patients not receiving reduced volume “boost” therapy:

Organs at risk (OAR) hard constraints:

- Bowel (including duodenum, large bowel): $V_{45} \leq 250 \text{ cc}$; $D_{\max} \leq 50 \text{ Gy (RBE)}$
- Rectum: $D_{\max} \leq 50 \text{ Gy (RBE)}$
- Bone Marrow: $V_{10} \leq 90\%$; $V_{20} \leq 75\%$
- Bladder: $D_{\max} \leq 50 \text{ Gy (RBE)}$
- Femoral Head: $D_{\max} \leq 50 \text{ Gy (RBE)}$
- Spinal cord: $D_{\max} \leq 36 \text{ Gy (RBE)}$
- Cauda: $D_{\max} \leq 50 \text{ Gy (RBE)}$
- Stomach: $D_{\max} \leq 42 \text{ Gy (RBE)}$
- Kidneys: $V_{18} \leq 30\%$ and $V_{10} \leq 50\%$ (for each kidney)

OAR soft constraints:

- Bowel: $V_{45} \leq 200 \text{ cc}$; $V_{40} \leq 30\%$; $D_{\max} \leq 45 \text{ Gy (RBE)}$

CONFIDENTIAL

This document is confidential. Do not disclose or use except as authorized.

- Rectum: $V_{45} \leq 50\%$; $V_{30} \leq 60\%$; $D_{max} \leq 50$ Gy (RBE)
- Bone Marrow: $V_{10} \leq 80\%$; $V_{20} \leq 66\%$
- Bladder: $V_{45} \leq 50\%$; $D_{max} \leq 50$ Gy (RBE)
- Femoral Head: $V_{30} \leq 15\%$; $D_{max} \leq 50$ Gy (RBE)
- Cauda Equina: $D_{max} \leq 42$ Gy (RBE)
- Kidneys: $V_{14} \leq 30\%$ (for each kidney)

For patients receiving reduced volume supplementary “boost” radiation:

- Small Bowel: $D_{max} \leq 52$ Gy (RBE)
- Large Bowel: $D_{max} \leq 56$ Gy (RBE)
- Cauda Equina: $D_{max} \leq 56$ Gy (RBE)
- Rectum: $D_{max} \leq 56$ Gy (RBE)
- Bladder: $D_{max} \leq 56$ Gy (RBE)
- Femoral Head: $D_{max} \leq 56$ Gy (RBE)

The deviations in dose constraints described are considered planning deviations only and will not constitute protocol deviations. Treatment plans that include minor planning deviations may be delivered as part of this protocol.

5.2.15 Vaginal brachytherapy will be administered on an outpatient basis employing standard techniques with high dose rate (HDR) remote afterloading equipment.

5.2.16 Cervix cancer patients will receive 3 brachytherapy fractions of 5 Gy each (15 Gy total) administered to the proximal 2 cm of the residual vagina with dose specified at the vaginal mucosa (surface of the intra-vaginal applicator).

5.2.17 Uterine cancer patients will receive 3 brachytherapy fractions of 5 Gy each (15 Gy total) to the proximal vagina with dose specified at the vaginal mucosa (surface of the intra-

CONFIDENTIAL

This document is confidential. Do not disclose or use except as authorized.

vaginal applicator). The full length of the vagina will be treated employing a gradient dose distribution such that the distal anterior sub-urethral vagina receives 3 Gy with each brachytherapy treatment.

5.2.18 For patients with cystocoele or rectocoele or vaginal introital diameter <2.5 cm, vaginal brachytherapy will be administered in 5 fractions of 3 Gy mucosal dose to the proximal vagina using techniques and dose distributions as specified in 5.2.13-5.2.15. Uterine cancer patients will have the distal vaginal dose administered in 5 fractions of 1.8 Gy.

5.2.19 Maximum point dose to the bladder and rectum from brachytherapy will be calculated and recorded from CT dosimetry from one insertion with applicator in the vagina. These dose contributions will not be applied to dose constraints in sections 5.2.13.

5.2.20 Other Modalities or Procedures:

5.2.20a Uterine cancer patients may receive conventional chemotherapy prior to proton radiation, with the drugs, doses and routes of administration to be selected by their attending Gynecologic Oncologist or Medical Oncologist. Uterine cancer patients will not receive concurrent chemotherapy with protocol teletherapy. All pre-radiation chemotherapy will be with commercially available agents approved for use with uterine cancer patients.

5.2.20b Cervical cancer patients may receive concurrent adjuvant cytotoxic chemotherapy with the drugs, doses and routes of administration to be selected by their attending Gynecologic Oncologist or Medical Oncologist. All chemotherapy will be with commercially available agents approved for use with cervical cancer patients.

5.2.20c Experimental or non-standard chemotherapy regimens will not be administered to study participants. All chemotherapy agents administered prior to or during study participation will be FDA approved agents commercially available.

5.2.20d For patients developing cancer recurrence after protocol therapy, investigational agents will not be precluded from their subsequent care.

